#### ED Study

**Patient Participants:** Because the patient's medical treatment is of foremost importance and to accommodate the fluid, unpredictable environments in the ED and to work within their usual flow, the researchers will pause all research procedures whenever necessary to allow for the patient's medical care and resume should there be additional periods of waiting. Once enrollment is complete (i.e., consent is obtained), the researchers will request a release of information from the participant for information we would like to gather from a member of their care team after the patient's discharge. Specifically, we are interested in collecting data about the patient's length of stay, if physical or chemical restraints were used and if so for how long, their final discharge disposition (e.g., if the patient was admitted to inpatient, residential, or substance abuse treatment or discharged to home), and if the patient was admitted whether it was involuntary or voluntary. This data will be obtained orally by speaking with a member of the patient's care team; medical records will not be accessed by the researchers. Permission (or not) for this release of information will not impact the patient's participation in the study (i.e., if they decline to provide permission for this release, they may still participate in the study). If the patient agrees to provide permission for the researcher to collect this information, they will be asked to sign a release of information form.

The researcher will then conduct the baseline assessment and the researcher will randomize the patient to condition while the participant is completing baseline measures. The researcher will inform the patient of the condition they have

been assigned after they have completed the baseline assessment.

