If the patient is assigned to the CAU condition, the researcher will conclude the session and tell the patient that they will return in two hours to complete the post treatment interview and online surveys. If the patient is assigned to the Jaspr condition, the researcher will walk the patient through a supplement consent form to provide further information about the app and obtain their electronic or paper/pencil signature. The researcher will orient the patient to the app on the study tablet, help them to set up their account, and let them know they may use Jaspr however they choose for up to two hours, not including breaks they may request or that may be needed in order to receive their standard medical care. The researcher will remain with the patient at all times while using Jaspr to answer any questions that the patient may have about Jaspr or the study; the researcher will not engage with the patient otherwise. After two hours of Jaspr use, the researcher will ask the patient to pause their use of Jaspr and conduct the post treatment interview and online surveys. If the patient indicates they are finished using Jaspr prior to the two hour timeframe, the researcher will conduct the post treatment interview and online surveys at that time. After the post treatment surveys are completed, researchers will orient the patient to installing the Jaspr-at-Home mobile app on their smartphone and ask them to use it however they see fit after being discharged. If the patient does not have access to their smartphone or if they prefer to install the app after they leave the ED, the researcher will provide email instructions for accessing and installing Jaspr-at-Home.

Patient participants will be asked to contact the researcher in the unlikely event that they are going to be discharged or transferred prior to completing the post treatment surveys so that the patient may complete the study procedures prior to leaving. Time spent completing the initial session (i.e., eligibility, consent, randomization, baseline, scheduling, and post assessment) is estimated to take approximately 2 – 4 hours depending on the number of breaks the patient is required or elects to take.

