After the post-treatment interview and surveys are completed in the ED, the onsite researcher will explain the purpose of blinding researchers to participants' condition and then virtually introduce (e.g., via Zoom, FaceTime) the patient participant to the (blinded) EBPI research assistant who will be responsible for conducting the post-discharge follow-up assessments. This research assistant will remain blind to the patient's condition during this discussion and the 7-, 30-, and most of the 90-day follow up assessment time points. At the very end of the 90-day assessment, the research assistant will be asking condition-specific questions (e.g., usability questions about the patient's experience with the Jaspr app) and thus cannot be blind during this assessment time point. In an effort to ensure a warm hand-off from the ED-based researcher to the follow-up blinded assessor, the blinded research assistant will schedule the three follow up assessments and administer the Participant Information Form.

Because the site contact or their designee will determine sufficiently stable participants to refer to the research, we do not anticipate that participation in the study will lead to significant distress. However, the researchers will be attentive to changes in mood states and, if indicated, will check in verbally with the participant about whether they wish to continue. If a participant becomes more distressed during the meeting for whatever reason (e.g., due to length of waiting in the ED, an upsetting conversation with medical personnel, or some aspect of the research procedure), the researchers will again ask if they prefer to discontinue the study. We prefer not to automatically discontinue the study in cases where their distress is caused by an aspect of their ED experience for the reason that participation in the study may actually be helpful to them in distracting them from the actual cause of their upset. We will however inquire about their preference to discontinue. We will also inform the site contact or their designee and a member of the patient's care team that the patient appears more upset than at the start of the research procedure. In cases where the patient appears more distressed than they were at the start of the procedure and displays difficulty redirecting to research tasks, we will discontinue the study procedure and notify the site contact or their designee and a member of the patient's care team.

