## **B. Analysis of Study Results**

During the summative evaluation, data gathered is qualitative and quantitative in nature. Online survey measures will be administered at four time points (baseline, post treatment, 7-day follow up, 30-day follow up, and 90-day follow up) to all ED study patient participants and three time points (baseline, 30-day, and 90-day follow up) to all Telehealth study participants. For the ED study, provider participants will complete study procedures via interview with the researcher (on paper or online if they prefer) at post treatment for all patients they treat as part of this study. Measures for patient

participants will include demographics, questions about suicidality, depressive symptoms, use of acute crisis tolerance skills, coping with acute distress, and satisfaction with ED experience. Measures for provider participants will include demographics, questions about preparedness for clinical interview, patient distress, provider confidence in suicide risk assessment, and helpfulness of Jaspr. Semi-structured interviews will be conducted with patient participants at each time point after baseline to obtain feedback about the participant's experience in the ED, experience with suicide symptoms, and/or Jaspr tools and features. For the Telehealth study, measures for patient participants include demographics, questions about suicidality, depressive and anxiety symptoms, stress, coping with acute distress, satisfaction with outpatient care and JAH. Semi-structured interviews at each follow-up assessment will be conducted to obtain feedback about the participant's experience with suicide and use of their resources since the prior study session.

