***Analysis Strategy.*** We will use SPSS Version 23. For patient data, we will use Hierarchical Linear Modeling (HLM). HLM provides greater flexibility in that it can analyze a variety of commonly encountered outcome distributions (e.g., continuous, binary count), test the fit of different covariance matrix assumptions; and include participants who are missing data at some time points. We will account for nesting of patients under providers by including providers as a random effect; we will account for nesting within sites by including dummy coded fixed effects predictors representing site in all analyses. For each outcome, we will specify the correct distribution and compare fit indices to identify the covariance matrix best fitting the data. Many hypotheses relate to change over time, and so the multiple time-points will be treated as nested within the individual. Also, we will treat the intervention conditions (Jaspr and JAH) and time as categorical, dummy-coded predictors; the control conditions and baseline scores will serve as the reference category. The parameter of interest will be the Time X Condition interaction, and the Type III statistic will serve as an omnibus test of whether the two conditions differed in change over time. Regression coefficients will indicate at which follow up time points the conditions showed differential change from baseline. For patient satisfaction as well as the secondary hypotheses concerning medical providers ratings of helpfulness, we will compute descriptive statistics and consider ratings to be favorable using the *a priori* established criteria that 80% or more respondents rate program components as favorable or highly favorable. For the remaining secondary hypotheses, which are based on provider data about patients from both conditions at one time point, we will compute between-condition means. Since it is possible that not all providers will be able to provide data given time constraints inherent in their job, we may not have the statistical power to conduct probability tests. Hence, we will examine the data descriptively to provide preliminary information about efficacy and compute effect sizes to inform future research.

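### ED study: the researcher randomises during baseline and can know the arm before the reference score for the Time X Condition tests is fixed

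*Combined protocol and SAP*

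**What the plan says.** Section 5.A, ED Study, gives the sequence. After consent, "The researcher will then conduct the baseline assessment", and in the same sentence "the researcher will randomize the patient to condition while the participant is completing baseline measures". The patient learns the condition they have "been assigned after they have completed the baseline assessment". The list of steps in the initial session also puts randomisation ahead of baseline: "eligibility, consent, randomization, baseline, scheduling, and post assessment".

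The only blinding described belongs to a different person, the follow-up assessor, who meets the patient after the post-treatment surveys: "This research assistant will remain blind to the patient's condition during this discussion and the 7-, 30-, and most of the 90-day follow up assessment".

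Section 5.B, Analysis Strategy, gives baseline its role. Time and condition are dummy-coded, and "the control conditions and baseline scores will serve as the reference category". It then states: "The parameter of interest will be the Time X Condition interaction".

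**The concern.** The order is a stated procedure, not a gap in the description. The person who draws the allocation later announces it, and no concealment step comes between. The natural reading is that this person knows the arm before baseline has closed.

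Section 5.A gives that researcher several judgement calls during sessions: pausing for care and resuming, answering questions, checking on mood, asking whether the patient wants to go on, and ending the procedure if a distressed patient cannot be redirected. Any of these that fall after the draw may be made with the arm known. They can affect the answers, and they can affect who finishes baseline.

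A shift introduced at baseline does not average out over the visits. It moves the point from which every later change is measured. It can exaggerate or hide an effect, depending on its direction.

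**Working it through.** **1. The sequence.** Three statements in 5.A, ED Study, bear on it. The researcher conducts baseline, the researcher randomises during baseline, and the patient is told after baseline. The third protects the patient's answers from the patient's own knowledge of the arm. None of the three withholds the arm from the researcher.

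**2. How a baseline shift enters the tested parameter.** Let b be an arm-related shift in mean baseline score, in SD units, with no true treatment effect. With baseline as the reference category, the interaction coefficient at visit t is

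(Jaspr at t − Jaspr at baseline) − (CAU at t − CAU at baseline) = 0 − b = −b.

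The full b appears at every follow-up visit.

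**3. The plan's own figure.** The plan gives 24 patients for a medium interaction effect (printed without its decimal point, read as f = 0.25), two-tailed alpha 0.05, power 0.80. It does not state the number of time points m or the correlation rho. Assume m = 4 and rho = 0.5:

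- lambda = f²·N·m/(1 − rho) = 0.0625 × 24 × 4 / 0.5 = 12, with 3 and 66 degrees of freedom.
- Power = 0.816, and N = 24 is reproduced.
- 24 × 3.0 = 72, and 72/0.8 = 90, as printed.

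The order of baseline and randomisation does not enter this calculation, so the sample size stands.

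**4. Sensitivity of one contrast.** The documents give no value for b, so a range is assumed. For one baseline-referenced contrast with n per arm, normal approximation and no clustering:

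- SE = √[2(1 − rho) × 2/n]
- Type I error = 1 − Φ(1.96 − b/SE) + Φ(−1.96 − b/SE)

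At n = 60 and rho = 0.5, SE = √(2/60) = 0.183. For b = 0.1, b/SE = 0.548 and the error is 0.085.

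| n per arm (source) | b = 0 | b = 0.1 | b = 0.2 | b = 0.3 |
|---|---|---|---|---|
| 36 (90 × 0.8 / 2) | 0.05 | 0.071 | 0.136 | 0.247 |
| 48 (120 × 0.8 / 2) | 0.05 | 0.078 | 0.165 | 0.312 |
| 60 (120 / 2) | 0.05 | 0.085 | 0.195 | 0.376 |

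With rho = 0.7 and 60 per arm the values are 0.109, 0.293 and 0.564. With rho = 0.5 and the plan's largest design effect applied (60/3.0 = 20 effective per arm, SE = √(2/20) = 0.316), they are 0.062, 0.097 and 0.158. The inflation is therefore sensitive to these assumptions, and its size depends mainly on b.

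**5. Which outcomes are exposed.** Only ED patient outcomes with a baseline score are exposed. Discharge disposition and restraint use come from the care team after discharge and rest on no baseline score. Provider ratings are taken at one time point.

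**6. The Telehealth study.** Section 5.A, Telehealth Study, includes randomisation in the enrolment call and schedules the baseline assessment at the end of that call. The whole of baseline therefore follows allocation.

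**The case against.** The case against is substantial, and much of it stands.

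- **The patient's answers are protected.** The patient does not know the arm during baseline. Section 7.B also limits what ED patients are told about Jaspr until after randomisation. Consent comes before the draw, so the timing cannot affect who enrols.
- **Baseline leaves little room for the researcher.** Section 5.B has the measures as online surveys ("Online survey measures will be administered at four time points (baseline, post treatment, 7-day follow up, 30-day follow up, and 90-day follow up") and places semi-structured interviews after baseline. The Introduction mentions an interview at the ED session, so a baseline interview is uncertain. Section 5.D says participants usually enter answers themselves, but it also allows direct entry by a research assistant, so the route is narrow rather than closed.
- **Knowledge of the arm is inferred.** The protocol does not say that the researcher sees the arm at that moment. The inference is strong, because the same person draws and announces it, but it remains an inference.
- **Incomplete baselines are partly handled.** The plan commits to intent-to-treat analysis and to a mixed model that keeps patients with missing visits. Such a patient stays in the analysis, though possibly without the reference score.

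A reader might go further in two ways that the documents do not support. One is to call a 0.1 SD shift a fifth of a medium effect, which takes medium as d = 0.5. The plan's medium effect is f = 0.25 on the interaction. With D the change contrast in SD units, f = D/4 for two time points, 0.2165·D for four with a constant follow-up difference, and 0.1863·D for a linear pattern over four. Setting f = 0.25 gives D = 1.0, 1.15 and 1.34, so 0.1 SD is about 7% to 10% of the planned effect. The other is to add chance imbalance between arms within sites. The documents do not say whether allocation is stratified, site is already a fixed effect, and imbalance is a different question from the timing of the draw.

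**Conclusion.** The point holds as an avoidable weakness in a stated procedure. As written, the ED researcher can know the arm before the reference score is complete, and a patient can be randomised without a full baseline. It would be too much to say that every Time X Condition test is exposed, or that bias has been shown.

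The likely size is small and the documents do not allow an estimate. The type I errors in the working describe what would follow from an assumed shift. They rest on an assumed correlation, a normal approximation and, except for the design-effect row of figures, independence between patients. The change is still worth making, because baseline anchors the main analysis and protecting it costs almost nothing.

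**What to change.** In 5.A, ED Study, state that the assignment is generated, or revealed to the researcher, only after the patient's baseline measures have been submitted and locked. Reorder the list of initial-session steps so that baseline comes before randomisation. If an interview does form part of ED baseline, say so and include it in what must be complete first.

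Apply the same order to the Telehealth study: complete and lock the baseline measures, then randomise, then begin the orientation that depends on the arm.

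The ED patient is already told the arm only after baseline, so the cost there is a short wait at that point. In the Telehealth study randomisation moves from the enrolment call to the baseline session. The sample size and the analysis model do not change.

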#### **D. Vulnerable Populations**

The risk to participants in this research is minimal when applying NIMH risk standards and designations. According to these NIMH guidelines, “minimal risk to subjects means that the probability and magnitude of harm or discomfort anticipated in the research are not greater than those ordinarily encountered in daily life or during the performance of routine physical and psychological examinations or tests and that confidentiality is adequately protected. This category includes protocols that pose “no greater than minimal risk” according to federal regulations.”

This study does include patients who are currently acutely suicidal and/or recently hospitalized because of suicidality. By definition, these patients are inherently high-risk participants; however, the question to consider for this research is whether the study procedures are likely to make the participants more suicidal. We believe the answer is no. Past research found that many of the patient participants enjoyed providing their feedback during the interview sessions and having their opinion/perspective valued. Some also described that for the moments they were interacting with the research team, their mind was off their worries. Preliminary data from our non-randomized observational research has demonstrated that suicidal patients feel less distressed following contact with our research team and use of Jaspr. Our research to date has demonstrated a 30% reduction in overall self-report ratings of distress for suicidal ED patients engaged in our research. Given the minimal risk nature of this study, the likely causes of such adverse events are likely to be factors related to their ED experience (e.g., nicotine withdrawal while in ED, fear/anxiety about what to expect, restrained on gurney, etc.) that co-occur or overlap with their engagement in our research, particularly during their ED stay. Unique research factors may include one or more of the following: length of the assessment, or interrupted use of Jaspr to attend to medical providers' interventions.

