### **C. Adverse Events**

For this study, we define an adverse event as any untoward or unfavorable occurrence, including significant increases in distress during the study interview, or symptom associated with the participant's participation in the research, *whether or not considered related to their participation in the research*. Serious adverse events include suicide attempt, non-suicidal self-injury, significant increase in suicidal ideation, and/or significant increase in agitation while participating in the study, as reported by the participant, or observed and/or reported by their healthcare provider, and/or a member of the research team. Given the minimal risk nature of this study, likely causes of such adverse events may include one or more of the following factors: frustration with the extensive length of stay in the ED (frequently considerably longer than the usual length of stay for patients with a medical crisis); nicotine withdraw caused from long lengths of stay in patients addicted to nicotine; and dissatisfaction with the care they are receiving while in the ED or with the discharge disposition provided by their physician.

Should adverse events occur during the study, we will thoroughly assess factors that contributed to the adverse event, including use of Jaspr or JAH, and will seek resolution of those problems related to the study. Regardless of the cause of the adverse event, we will notify the IRB and our DSMB of adverse events within 10 business days, should they occur, and seek their recommendations. Fatal or life-threatening events, should they occur, will be reported to the IRB.

immediately.

All participants will be provided with information about how to report Potential Adverse Events. In addition, patient participants will be encouraged to report any Potential Adverse Events directly to the provider who is in charge of their care. Potential Adverse Event reports will be monitored daily by study staff. Because the risks to participation are low, the likelihood of Adverse Events related to the proposed research is judged to be low. In the event that a Potential Adverse Event is reported, the PI will be notified immediately. The PI will then assess the situation and determine an appropriate clinical and ethical course of action, including report of an Adverse Event to the IRB and DSMB.

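### Between disclosure of assignment and the post-treatment interview in the ED, only Jaspr patients are under researcher observation, so researcher-observed events, care-team notices and distress-related stopping can arise in that window in one arm only

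*Combined protocol and SAP*

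**What the plan says.** Section 5.A (Summary of the Research Design, ED Study, Patient Participants) treats the arms alike through consent and baseline. The sentence that marks the split begins "The researcher will inform the patient of the condition they have" and places this after the baseline assessment.

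From there the arms differ. For CAU, "the researcher will conclude the session and tell the patient that they will return in two hours". For Jaspr, patients are told that "they may use Jaspr however they choose for up to two hours, not including breaks", they may finish sooner, and "The researcher will remain with the patient at all times while using Jaspr". Both arms then have the post-treatment interview and surveys.

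The same section has researchers watch for changes in mood, ask a more distressed participant whether to discontinue, and tell the site contact and care team. If the patient is more distressed than at the start and "displays difficulty redirecting to research tasks, we will discontinue the study procedure". The hand-off to the blinded assessor, who books the 7-, 30- and 90-day assessments, comes after the post-treatment interview and surveys.

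Section 6.C (Adverse Events) counts a significant rise in agitation during participation as serious, whether reported by the participant or "observed and/or reported by their healthcare provider, and/or a member of the research team". Section 5.B (Analysis of Study Results) plans to collect data from everyone at every time point, including those who stop using Jaspr.

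**The concern.** An event can be recorded by a researcher only when a researcher is there. If one arm is watched for up to two hours and the other is not, researcher-observed counts can differ with no difference in risk. That would make Jaspr look less safe in any by-arm summary, including the material that section 5.C (Monitoring) sends to the DSMB, which may recommend stopping.

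Two further consequences bear on outcomes that section 3 lists as primary for the ED study:

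- Telling the care team that a patient looks more upset could influence restraint use or disposition. In this window only Jaspr patients can trigger such a notice.
- A Jaspr patient stopped mid-app may give no post-treatment rating of acute distress or coping self-efficacy. That would tend to remove poor ratings from the Jaspr arm, a bias in favour of the app and so opposite in direction to the one on safety counts.

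**Working it through.** The plan states no figure on this point, so there is none to reproduce. The check compares the procedures and then shows a range under stated assumptions.

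**1. Researcher presence by stage (section 5.A)**

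| Stage | Jaspr | CAU |
|---|---|---|
| Consent and baseline | present | present |
| Disclosure of condition to post-treatment interview | present during app use, up to 2 h | absent, 2 h |
| Post-treatment interview and surveys | present | present |

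Each distress rule needs a researcher to see the patient, and mandatory stopping also needs a research task in progress. In the middle row CAU patients have neither. In the other two rows the rules apply to both arms.

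**2. Researcher contact after disclosure**

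Jaspr = use + post-treatment contact; CAU = post-treatment contact. The two-hour maximum is in the protocol. The length of post-treatment contact is not, so 0.25, 0.5 and 1.0 h are assumed. The half-hour use is also assumed.

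| Use (h) | Post (h) | Jaspr : CAU (h) | Ratio | Jaspr share |
|---|---|---|---|---|
| 2 | 0.25 | 2.25 : 0.25 | 9 | 90% |
| 2 | 0.5 | 2.5 : 0.5 | 5 | 83% |
| 2 | 1.0 | 3.0 : 1.0 | 3 | 75% |
| 0.5 | 0.25 | 0.75 : 0.25 | 3 | 75% |
| 0.5 | 0.5 | 1.0 : 0.5 | 2 | 67% |
| 0.5 | 1.0 | 1.5 : 1.0 | 1.5 | 60% |

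Add an assumed 0.5 to 1 h of shared consent and baseline contact per arm, with two hours of use. The Jaspr share of all researcher contact is then between (3.0 + 1)/(3.0 + 1.0 + 2) = 67% and (2.25 + 0.5)/(2.25 + 0.25 + 1) = 79%. Supplementary consent, app orientation and help with the take-home app are further Jaspr-only contact, not counted here.

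**3. What equal true risk could look like**

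Assume a constant rate r of observable events per hour in both arms, full two-hour use, 0.5 h of post-treatment contact, 60 patients per arm (section 3), and that a researcher who is present sees every event. Patients with a researcher-observed event = 60 × (1 − exp(−r × hours)).

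- r = 0.05: Jaspr 60 × (1 − exp(−0.125)) = 7.1; CAU 60 × (1 − exp(−0.025)) = 1.5.
- r = 0.02: 2.9 against 0.6.
- r = 0.10: 13.3 against 2.9.

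The rates are assumptions. The example shows direction and is not an estimate for this trial.

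**4. What happens after a procedure is stopped**

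Section 5.A asks patients about to be discharged or transferred early to contact the researcher so that they can finish. It gives no matching route for a patient stopped for distress. Since the follow-up hand-off comes after the post-treatment surveys, a patient stopped mid-app has no stated path to the post-treatment rating or to the booking of follow-up. Section 5.B intends those data but gives no procedure for this case. Section 5.B favours methods whose assumptions, such as missing at random, are plausible. If distress rose after baseline and was never rated, the missing value depends on something unobserved, and a mixed model does not by itself repair that.

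**The case against.** The strongest reply is that much of the ED contact and reporting is common to both arms. The distress rules are written for any participant, so a CAU patient who is distressed at the post-treatment meeting comes under the same rule. Participants and providers can report serious events in either arm, and section 6.C's distress example is tied to the study interview, which both arms have. Section 3.C reports that ED staff keep patients under observation. Enrolled providers in both arms are asked for a post-treatment interview that covers patient distress, and patients complete surveys at baseline and post-treatment. No between-arm test of adverse events is planned. Section 5.A prefers not to stop automatically when the ED experience is the cause of distress.

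All of this stands, and it limits the point without removing it. The provider interview asks about distress at the encounter, not worsening since baseline, and section 5.B expects that some providers may not supply data. The DSMB still receives a detailed summary of potential adverse events.

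Four stronger readings are tempting, and the documents do not support them:

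- A reader might infer that the distress rules work almost exclusively in the Jaspr arm over the whole ED stay. Baseline and post-treatment contact rule that out.
- A reader might infer that stopped patients are withdrawn. The text stops the study procedure, and section 5.B plans data from all.
- A reader might express the loss as a fraction of the medium effect in the power section. That needs assumed stopping rates and a complete-case mean, ignores the mixed model, and sets a single-time difference against an f for the Time × Condition interaction.
- A reader might take section 4.D's remark that "suicidal patients feel less distressed following contact with our research team and use of Jaspr" as evidence that researcher contact lowers distress. It is uncontrolled and joins contact with app use, and section 5.A limits the researcher during use to answering questions.

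**Conclusion.** The point holds in a limited form and merits a change. From disclosure of assignment to the post-treatment interview, researcher-observed events, researcher notices to the care team and distress-related stopping can arise only in the Jaspr arm, and nothing in the protocol equalises or adjusts for this. Outside that window the arms are treated alike. The two-hour contrast (up to 2 h against none) comes from the protocol; the ratios of 1.5:1 to 9:1 and the event counts rest on assumed durations and rates, so the size of any bias cannot be computed from the documents. Loss of post-treatment ratings from distressed patients is possible and more likely in the Jaspr arm, but it is not a stated procedure.

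**What to change.** 1. At the post-treatment contact, ask patients in both arms the same short question on marked worsening of distress or agitation since baseline, and add the same item to the existing provider interview. Use these common sources for any by-arm summary of in-ED adverse events, including DSMB reports. Record the source of every event, and list separately those seen only by the researcher during app use.
2. In section 5.A, state, in line with section 5.B, that stopping a procedure for distress ends only that procedure. Unless the patient chooses to leave the study, the post-treatment assessment is offered again before ED departure, and the 7-, 30- and 90-day assessments are booked and kept, in both arms. The criteria for stopping a procedure are unchanged.

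The cost is two added items and some protocol wording. Some post-treatment assessments will be taken later than planned, so their actual time should be recorded.
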